9.3. Variables

Baseline variables (Table 2) will be measured during the baseline period (365 days prior to the index date). Treatment patterns, adherence and persistence, and clinical variables (Table 3) will be measured during the follow-up period.

Table 2. Baseline demographic and clinical characteristic variables

Variable	Operational definition
Age	Age will be defined as of the index date and retained in the dataset as a continuous variable and a categorical variable (e.g., ≤ 59 , 60-69, 70-79, ≥ 80 years old).
Race/ethnicity	Proportion of patients that were non-Hispanic White, Black, Hispanic, other or unknown will be summarized.
Geographic regions	Proportion of patients that lived in Northeast, Midwest, South and West areas will be summarized.
Index year	A categorical variable for the index calendar year will be summarized.
Site of metastasis	Proportion of patients that had a metastatic diagnosis at the following sites: bone only, bone and node only, node

PFIZER CONFIDENTIAL

Variable	Operational definition
	only, viscera and other, will be summarized among patients with metastatic PC. All data available prior to the index date will be used.
Treatment history	
Proportion of patients who had each of the following treatments in the baseline period will be evaluated:
 
• Prostatectomy• Chronic oral corticosteroid use• Pain medication (opioids)• ADT treatment (leuprolide, degarelix, goserelin, histrelin, triptorelin)• Androgen receptor pathway inhibitor (ARPI; abiraterone, apalutamide, darolutamide, enzalutamide)• Non-steroidal anti-androgen (NSAA; bicalutamide, nilutamide, flutamide)• Chemotherapy (docetaxel, cabazitaxel, carboplatin, oxaliplatin, cisplatin, mitoxantrone)• Immunotherapy (sipuleucel-T, pembrolizumab)• Radium 223• Systemic ketoconazole• Olaparib• Rucaparib• Talazoparib• Niraparib• Lutetium Lu 177 vipivotide tetraxetan• Radiotherapy 
Treatments considered as a part of index treatment regimen will not be flagged as baseline treatments if received within 30 days prior to index date.

Time from first observed PC diagnosis date to the index date	Time from the first observed PC date in the data to the index date will be evaluated. All data available prior to the index date will be used.
NCI Charlson Comorbidity Index (CCI) score	The NCI version of the CCI score will be created during the baseline period.

Variable	Operational definition

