Appendix Table 2. Diagnosis codes for comorbidities

Conditions and comorbidities	ICD-10-CM
NCI comorbidity index¹	
Cerebrovascular disease	G45, G46, H34.0, I60–I69
Chronic pulmonary disease	I27.8, I27.9, J40–J47, J60– J67, J68.4, J70.1, J70.3
Congestive heart failure	I09.9, I11.0, I13.0, I13.2, I25.5, I42.0, I42.5–I42.9, I43, I50, P29.0
Dementia	F00–F03, F05.1, G30, G31.1
Diabetes with chronic complication	E10.2–E10.5, E10.7, E11.2– E11.5, E11.7, E12.2–E12.5, E12.7, E13.2– E13.5, E13.7, E14.2–E14.5, E14.7
Diabetes without chronic complication	E10.0, E10.1, E10.6, E10.8, E10.9, E11.0, E11.1, E11.6, E11.8, E11.9, E12.0, E12.1, E12.6, E12.8, E12.9, E13.0, E13.1, E13.6, E13.8, E13.9, E14.0, E14.1,

PFIZER CONFIDENTIAL

CT24-WI-GL02-RF02 5.0 Non-Interventional Study Protocol Template For Secondary Data Collection Study 01-Aug-2023
Page 37 of 41

	E14.6, E14.8, E14.9
Hemiplegia or paraplegia	G04.1, G11.4, G80.1, G80.2, G81, G82, G83.0–G83.4, G83.9
Mild liver disease	B18, K70.0– K70.3, K70.9, K71.3–K71.5, K71.7, K73, K74, K76.0, K76.2–K76.4, K76.8, K76.9, Z94.4
Moderate or severe liver disease	I85.0, I85.9, I86.4, I98.2, K70.4, K71.1, K72.1, K72.9, K76.5, K76.6, K76.7
Peripheral vascular disease	I70, I71, I73.1, I73.8, I73.9, I77.1, I79.0, I79.2, K55.1, K55.8, K55.9, Z95.8, Z95.9
Renal disease	I12.0, I13.1, N03.2–N03.7, N05.2–N05.7, N18, N19, N25.0, Z49.0– Z49.2, Z94.0, Z99.2
Individual conditions	

PFIZER CONFIDENTIAL

CT24-WI-GL02-RF02 5.0 Non-Interventional Study Protocol Template For Secondary Data Collection Study 01-Aug-2023

Page 38 of 41

Hypertension	H35.039, I10–I13, I15–I16, I67.4
Hyperlipidemia	E78.00, E78.01, E78.1, E78.2, E78.3, E78.41, E78.49, E78.5
Type II diabetes	E10.0, E10.1, E10.6, E10.8, E10.9, E11.0, E11.1, E11.6, E11.8, E11.9, E12.0, E12.1, E12.6, E12.8, E12.9, E13.0, E13.1, E13.6, E13.8, E13.9, E14.0, E14.1, E14.6, E14.8, E14.9
Urinary tract infection	
Chronic obstructive pulmonary disease	J40, J41, J42, J43, J47, J44.9
Arrhythmia	I47.0, I47.2, I49.0, I46, I49.3, I49.49, I47.9, I49.40, I49.5, I49.8, I49.9
Congestive heart failure	I09.9, I11.0, I13.0, I13.2, I25.5, I42.0, I42.5–I42.9, I43, I50, P29.0
Myocardial infarction	I21, I22, I25.2

Stroke	I60, I61, I62, I64, I65, I67, H34.1, H34.23, H34.21, H34.0
Angina pectoris	I20
Inflammatory bowel disease	K50, K51
Acute coronary syndrome	I24, I21
Sexual dysfunction	F52.21, N52
Depression	F20.4, F31.3- F31.5, F32, F33, F34.1, F41.2, F43.2
Anxiety	F06.4, F41, F43.22, F43.23, F93.0

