Cognitive impairment	G30, G31.0, F01, F05, R41.0, R41.82, F10.1, F10.2, G31.2, G31.83, F02, F03, G31.1, G31.84, F06.7, R41.3, R41.81, R41.840
Hot flashes	R23.2
Primary cancers	C00-C21, C22.1-C22.7, C23-C76, C80.1, C80.2, C81-C96, C7A

Abbreviations: ICD-9-CM: International Classification of Diseases, 9th Revision, Clinical Modification; ICD-10-CM: International Classification of Diseases, 10th Revision, Clinical Modification; NCI: National Cancer Institute

[1] Source: Quan, Hude, et al. Coding algorithms for defining comorbidities in ICD-9-CM and ICD-10 administrative data. Medical care (2005): 1130-1139. Adapted using codes found in NCI Comorbidity Index Overview: <https://healthcaredelivery.cancer.gov/seermedicare/considerations/comorbidity.html>

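### The code list for the NCI Charlson score has no row for myocardial infarction, peptic ulcer, rheumatic disease or HIV/AIDS, and no weights are stated

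*Combined protocol and SAP*

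**What the plan says.** Section 9.3, Table 2 gives the score one line: "The NCI version of the CCI score will be created during the baseline period". It names no component conditions and no weights. Annex 1 lists no stand-alone documents, so nothing else in the plan defines the score.

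Annex 2, Appendix Table 2 has a block headed "NCI comorbidity index", followed by a second block headed "Individual conditions", which holds the codes for the separate comorbidity flags. Myocardial infarction appears only in the second block, with codes I21, I22 and I25.2. Footnote 1 gives the origin of the index codes as a published coding algorithm, with the remark "Adapted using codes found in NCI Comorbidity Index Overview". It reproduces the component list of neither source and does not say that any condition was dropped.

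**The concern.** A score called the NCI version of the Charlson index would be expected to credit a previous myocardial infarction, which is a basic component of the Charlson instrument. A programmer who follows Appendix Table 2 literally would give no credit for it, nor for peptic ulcer, rheumatic disease or HIV/AIDS.

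The score is used in several places. The Abstract names it as a baseline characteristic, so it is part of the primary objective. Section 9.7.1 may compare it between metastatic and non-metastatic patients by standardized mean difference. Section 9.7.5 compares it between Black and non-Hispanic White patients with p-values and, if sample sizes allow, standardized mean differences. Sections 9.7.6 and 9.7.7 draw the covariates of the adjusted models from those findings and clinical input. A score built on an undeclared subset would be reported under a standard name in all of them.

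**Working it through.** The plan states no component count, weight or prevalence, so there is no figure of its own to reproduce. The check compares the two blocks of Appendix Table 2.

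1. **Count of rows in the index block.** Cerebrovascular disease, chronic pulmonary disease, heart failure, dementia, diabetes (2 rows), hemiplegia or paraplegia, liver disease (2 rows), peripheral vascular disease, renal disease: 1 + 1 + 1 + 1 + 2 + 1 + 2 + 1 + 1 = 11.

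2. **Do the infarction codes fall inside any of the 11 rows?** I21, I22 and I25.2 were tested against every code and range in the block. None matches. The nearest code is I25.5, under heart failure. A man whose only coded condition is a myocardial infarction therefore scores nothing from this block.

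3. **Are the other three conditions coded elsewhere?** No. Peptic ulcer, rheumatic disease and HIV/AIDS have no codes anywhere in the documents.

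4. **How does the appendix treat a condition that is both a component and a flag?** It lists it twice. The heart failure codes are identical in both blocks, and the codes for diabetes without chronic complication reappear unchanged under type II diabetes. Infarction is listed once, outside the index. By the table's own convention, that places it outside the score.

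5. **Could rows have been lost in the PDF text?** The block is alphabetical.
   - It opens with cerebrovascular disease ("G45, G46, H34.0, I60–I69"), with no row for AIDS before it. There is also no row for HIV between hemiplegia and mild liver disease.
   - Infarction and peptic ulcer would fall after "Moderate or severe liver disease" ("I85.0, I85.9, I86.4, I98.2, K70.4, K71.1, K72.1, K72.9, K76.5, K76.6, K76.7"), but the next row is peripheral vascular disease.
   - Rheumatic disease would follow renal disease ("I12.0, I13.1, N03.2–N03.7, N05.2–N05.7, N18, N19, N25.0, Z49.0– Z49.2, Z94.0, Z99.2"), but the next line is the heading of the second block.
   - No page footer stands at any of these places. The page 37 footer falls inside a diabetes row, and the page 38 footer comes after the second heading. Lost rows are not indicated.

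6. **Illustration of size, on assumed inputs only.** For one omitted condition, shift in mean score = weight × prevalence. With an assumed weight of 0.1 to 1 and an assumed prevalence of 2% to 15%:
   - lowest: 0.1 × 0.02 = 0.002
   - highest: 1 × 0.15 = 0.15

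   For an individual man with that condition, the shortfall is its full weight.

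**The case against.** The strongest reply is that the component list of the NCI version lies in two cited sources that the plan does not reproduce, and that the footnote says the codes were adapted. A deliberate subset is therefore possible. This stands: the documents do not prove that all four conditions belong to the NCI version, and a reader should not infer a fixed number of missing components. It does not remove the point, because an intended subset is nowhere declared and the score carries the standard name.

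A second reply is that the infarction codes are in the same table and could feed the score. The plan does not say that they do, and the double listing of heart failure and diabetes suggests that they do not.

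A third reply is that little is lost: the primary objective is descriptive, infarction is reported as its own flag and within the major adverse cardiovascular event variable, and the score is not a named covariate. This limits the consequence. It does not cover the other three conditions, which have no flag, and it does not correct the reported score.

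On extraction, the page markers in the annex are incomplete (none for pages 36 or 39) and one code cell in the same table is empty. Lost rows are therefore unlikely rather than excluded.

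**Conclusion.** The point holds in a conditional form. As written, the only operational definition of the score has 11 conditions and none of the four named. If the score is built from that block, it is understated for any man with an omitted condition that carries positive weight. This rests on two assumptions: that the block is complete as printed, and that the NCI version gives the condition a weight above zero. The case is clearest for infarction, whose codes the plan already holds.

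A reader might go further and infer that the score is too low for every man with any of the four, by a known amount, and differently by race. The documents do not support this. They give no weights and no prevalences, so the range of 0.002 to 0.15 points for one condition is illustration only. They show no difference between Black and non-Hispanic White patients in the omitted conditions. The score enters the adjusted models only if it is selected.

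**What to change.** In Appendix Table 2, add a myocardial infarction row to the index block with the existing codes I21, I22 and I25.2. Check peptic ulcer, rheumatic disease and HIV/AIDS against the two sources in footnote 1, and add a row for each condition that those sources include. In Table 2, list the components and state the weights. If any condition is left out on purpose, say so with the reason, and report the result as a modified NCI CCI.

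The cost is a few code rows and a few sentences. No new data are needed, since the diagnosis codes come from the same 365-day baseline records.

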9. RESEARCH METHODS

9.1. Study design

This is a retrospective, observational study using January 1, 2006 – December 31, 2023 data from the National VA Health Care Network databases. PC patients who initiated relugolix will be selected based on diagnosis codes, age, treatment received, and continuous activity in the health care network. The identification period for relugolix use will be from December 18, 2020 to December 31, 2023. December 18, 2020 is the approval date for relugolix in the US, and December 31, 2023 is the end of available data. The index date will be defined as the initiation date of relugolix. The baseline period will be 365 days prior to the index date (hence the start of the study period is December 18, 2019). The follow-up period will be from the index date to the earliest of death, end of continuous eligibility or end of data availability. Most of the patient characteristics will be described during the baseline period. Certain patient characteristics will be described using all data available prior to the index date (i.e., data prior to December 18, 2019 will also be used if available; see more details in Table 2). Treatment patterns, adherence, and persistence with relugolix, and PSA and testosterone responses (if sample size allows) will be assessed during the follow-up period.

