Comorbidities	A binary variable (yes/no) will be created for patients with a diagnosis of each of the following comorbidities during the baseline period: 
• Hypertension• Hyperlipidemia• Diabetes• Urinary tract infection• Chronic obstructive pulmonary disease• Arrhythmia• Congestive heart failure• Myocardial infarction• Stroke• Angina pectoris• Inflammatory bowel disease• Acute coronary syndrome• Sexual dysfunction• Depression• Anxiety• Hot flashes• Cognitive impairment• Major adverse cardiovascula event (defined by any evidence of cardiomyopathy, heart failure, ischemic heart disease, myocardial infarction, pulmonary embolism, or stroke)
PSA	Baseline PSA value (among available) based on the PSA value closest to the index date during the 90-day window (or 180-day, to be finalized based on the number of patients with non-missing PSA value in these time frames) on or prior to the index date will be evaluated.
Testosterone	Baseline testosterone value (among available) based on testosterone value closest to the index date during the 90-day window (or 180-day; will be consistent with the time window for baseline PSA) on or prior to the index date will be evaluated.
Metastatic vs. non-metastatic PC	A binary variable for patients with metastatic vs. non-metastatic PC will be created. Metastatic PC will be

Variable	Operational definition
	defined as having evidence of metastasis during the baseline period or within 90 days since the index date.
ADT naïve vs. ADT experienced	A binary variable for patients who were ADT naïve vs. ADT experienced will be created. ADT naïve will be defined as having no records of any systemic ADT treatment ever based on all available data prior to the index date (i.e., including baseline period data and any available data prior to the baseline period). Systemic ADT treatment includes LHRH agonists and GnRH antagonists (i.e., degarelix, relugolix, goserelin, histrelin, leuprolide, triptorelin)

Table 3. Treatment patterns, adherence, persistence, and clinical variables during the follow-up period

Variable	Operational definition

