Index treatment	
Index treatment regimens include:
 
 • Relugolix monotherapy • Relugolix + NSAA only (at least 90 days of NSAA use) • Relugolix + ARPI +/- NSAA (no chemotherapy) • Relugolix + ARPI + chemotherapy • Relugolix + chemotherapy +/- NSAA (no ARPI) • Relugolix + other (no ARPI, no chemotherapy) 
Index treatment regimen will be defined based on treatments received within 30 days before the index date and within 90 days after the index date.
 
Specific treatments included in each treatment category (i.e., ADT, NSAA, ARPI, chemotherapy, immunotherapy) are described in “Treatment history” in Table 2. Other treatments include immunotherapy, radium 223, olaparib, rucaparib, talazoparib, niraparib and lutetium Lu 177 vipivotide tetraxetan.
 
Number of patients who received any radiotherapy during the index treatment will be summarized.

Variable	Operational definition
Treatment patterns of relugolix	
Treatment patterns of relugolix include:
 
• Continued relugolix as in the index treatment (regardless of discontinuation of concomitant medications)• Continued relugolix with a new add-on systemic PC treatment (excluding ADT)• Discontinued relugolix and switched to another ADT treatment• Discontinued relugolix without switching to another ADT treatment 
Add-on systemic PC treatments include:
 
• ARPI• NSAA• Chemotherapy• Immunotherapy• Radium 223• Ketoconazole• Olaparib• Rucaparib• Talazoparib• Niraparib• Lutetium Lu 177 vipivotide tetraxetan 
Add-on therapy will be evaluated from 90 days after the index period to the end of the follow-up period.

Time to treatment changes	The time to treatment changes of interest include: 
• Time to discontinuation of relugolix• Time to switching to a different ADT treatment• Time to add a new systemic PC treatment to relugolix
Treatment adherence	Adherence to relugolix post the index date will be described using both MPR and PDC: 
• MPR: Sum of the days of supply divided by the number of days between the first fill and the end of the last refill (i.e., including the days of supply from the last refill)• PDC: Sum of the non-overlapping (i.e., not double counting of overlaps) days of supply covered

Variable	Operational definition

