9.7. Data analysis

9.7.1. Data analysis for Objective 1: To describe demographics and clinical characteristics of patients with PC who initiated relugolix

Descriptive analysis will be conducted for baseline demographics and clinical characteristics. Means, standard deviations, medians, and interquartile range will be estimated for continuous variables. Counts and percentages will be estimated for categorical variables. If the sample sizes allow, standardized mean difference (SMD) will be calculated to compare the patient baseline characteristics between metastatic vs. non-metastatic PC cohorts. For each variable, the SMD will be calculated as the difference in mean between two cohorts divided by the standard

deviation of the two cohorts pooled together. The absolute value of a SMD $> 10\%$ will be considered as an indicator for significant imbalance.

9.7.2. Data analysis for Objective 2: To assess treatment patterns among patients with PC who initiated relugolix

[figure not shown]

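### Table 2 counts metastasis evidence up to 90 days after index when flagging metastatic PC, but ignores it when assigning site of metastasis

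*Combined protocol and SAP*

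**What the plan says.** Two rows of Table 2 (Section 9.3) deal with metastasis.

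- **Metastatic vs. non-metastatic PC.** Metastatic PC is "defined as having evidence of metastasis during the baseline period or within 90 days since the index date".
- **Site of metastasis.** The proportions in each site group "will be summarized among patients with metastatic PC. All data available prior to the index date will be used".

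Section 9.3 opens with a general rule that Table 2 variables come from the 365-day baseline. Both rows depart from it, in different directions: status reaches forward past the index date, and site reaches back without limit but stops before the index date. Section 9.1 gives notice of the longer look-back: "Certain patient characteristics will be described using all data available prior to the index date". It does not mention post-index data for any patient characteristic.

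The status flag is used again in Section 9.7.1, where, if sample sizes allow, SMDs will "compare the patient baseline characteristics between metastatic vs. non-metastatic PC cohorts". Section 9.7.5 repeats the baseline description by race.

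**The concern.** The status row decides who is in the site table, and the site row decides what is reported for them. If the first accepts evidence that the second refuses, some patients enter the denominator without anything to fill the numerator.

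Three of the site groups (bone only, node only, bone and node only) also assert that no other site is involved. Such a label is only as good as the evidence searched. Leaving out a period that the plan itself treats as valid evidence of metastasis can put a patient in the wrong group.

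Both variables belong to the primary objective, which is purely descriptive, so the definitions determine the result.

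**Working it through.** No figure in the plan is at issue, so the check sets the two definitions side by side. Divide time into A = before day -365, B = day -365 to -1, and C = day 0 to +90. Day 0 is placed in C because the site row takes only data before the index date. Status is metastatic if there is evidence in B or C. Site is read from A and B.

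| Evidence in | Status | Site as written | Site with C added |
|---|---|---|---|
| none | non-metastatic | not in table | not in table |
| A only | non-metastatic | not in table | not in table |
| B only | metastatic | from B | from B |
| A, B | metastatic | from A, B | from A, B |
| C only | metastatic | none available | from C |
| A, C | metastatic | from A; C ignored | from A, C |
| B, C | metastatic | from B; C ignored | from B, C |
| A, B, C | metastatic | from A, B; C ignored | from A, B, C |

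Six of the eight patterns are flagged metastatic. As written, 1 has no site, 3 may have an incomplete site, and 2 are unaffected (1 + 3 + 2 = 6). With C added, none of the six lacks a site, or has an incomplete one, because of the window. These are counts of patterns, not of patients.

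Example: bone metastasis recorded on day -200 and visceral metastasis on day +30. The plan as written reports bone only. With C added, the visceral record counts.

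**Size of the missing-site effect.** If a fraction f of flagged patients have evidence in C only and are given no site, the site percentages sum to 1 - f. The documents give no f. For assumed values of 2% and 10%, the sums are 98% and 90%.

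**The A-only pattern.** These patients have a record in the period that the site row searches but are classed non-metastatic. Let p be the truly metastatic share and x the fraction of those with A-only evidence. The reported share is p(1 - x), and the share of the non-metastatic column that is metastatic is c = px/(1 - p + px). Neither input is in the documents. Assume p = 0.3 or 0.5:

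- x = 0.05: c = 0.015/0.715 = 2.1% or 0.025/0.525 = 4.8%.
- x = 0.20: c = 0.06/0.76 = 7.9% or 0.10/0.60 = 16.7%.

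The plan's SMD divides by the standard "deviation of the two cohorts pooled together". Read as the SD of the combined sample, this does not change when patients move between cohorts. The observed SMD is then the true one times (1 - c), if the missed patients have the metastatic mean. A reading of 0.10 would correspond to 0.10/(1 - c): 0.102 or 0.105 for x = 0.05, and 0.109 or 0.120 for x = 0.20. This illustration also assumes that every older record is true.

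**The case against.** The best defence is that this is a deliberate two-step design: decide status on recent evidence, then describe the flagged patients' sites from their full history. Section 9.1 announces mixed look-backs. The 90-day extension matches the index regimen, which is based on "treatments received within 30 days before the index date and within 90 days after the index date". A short look-back for status also limits rule-out and miscoded diagnoses, which Section 9.9 names as a limitation. All of this stands as a reason to leave the status definition alone. None of it explains why the site row drops the 90 days that helped to set its own denominator.

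It can also be said that the site groups are not declared exhaustive, and that the group for other sites could absorb patients without one. The plan does not say so, and doing it would report an unknown site as a known one. It would not help patients placed in the wrong exclusive group.

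A reader might go further and infer that the two rows disagree on who is metastatic. They do not: only the status row defines metastatic PC, and the site row borrows that denominator. A reader might also infer that the metastatic proportion is too low because older evidence is ignored. That would need the older records to be true and the flag to have no offsetting false positives, and Section 9.9 supports neither. The ADT-naïve row, with "no records of any systemic ADT treatment ever based on all available data prior to the index date", is a weak precedent for a full look-back on status, because never having been treated can only be judged on full history.

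**Conclusion.** The mismatch between the windows is clear on the face of the text, and nothing else in the documents reconciles it. As written, patients with evidence only on day 0 to +90 have no assignable site, and sites first recorded in that window are lost for the others. This rests on the wording of the two rows and on reading day 0 as outside the pre-index data. It does not depend on any assumed rate.

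The number of patients affected is not computable from the documents and may be small. Data start in 2006, so a reader might take the long stretch of history searched for site but not for status as a measure of impact. Calendar days are not patients: if metastases are recorded again each year, few patients would have older evidence only. The 365-day look-back for status is a defensible choice and calls for a sensitivity count, not a new definition. Under the assumed inputs above, its effect on the SMD is modest.

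**What to change.** 1. In the Site of metastasis row, take evidence from all pre-index data plus day 0 to +90, so that the window covers everything that can make a patient metastatic.
2. Add a 'site not recorded' row for flagged patients who still have no identifiable site.
3. Keep the status definition. Report as a sensitivity count the patients whose only metastasis evidence lies before day -365, and show the metastatic proportion, and the SMD comparison if it is done, with them reclassified.

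The cost is one changed definition, one table row and one sensitivity display; data from 2006 are already in scope. The longer look-back in item 3 may pick up some rule-out or miscoded records, which is why it is offered as a sensitivity count beside the main definition. Changing status to pre-index data only would also align the rows, but it would move patients with post-index evidence only out of the metastatic group. Extending the site window avoids that.
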